4.9 Data collection

Data for IPD cases is extracted from existing surveillance database or from hospital discharge databases. In countries or regions with a unique identifier, investigators can link various databases. For each variable, the database source and its characteristics should be defined. A table like Table 3 presented at the end of the document can be adapted and completed to summarise the sources for each of the variables to be extracted and included in the analysis.

► Each study site to specify the list of variables to be extracted.

4.10 Data management

- ► Each study site to describe all procedures for data management:
 - Who extracts data?
 - Who validates data?
 - How, by whom and when are data stored?
 - Who links databases?
 - How are data extracted?
 - Who analyses data?
 - Softwares used?
 - How and who do the anonymization of the database to be used in the analyses?

5. Analysis

5.1 Data checking

As much as possible, data should be completed or validated against the data source. Data will be checked to find outliers, implausible or missing information. The inclusion and exclusion criteria will be checked for the studies using IPD surveillance. If the following variables are missing, cases will be excluded:

- Date of birth/ age;
- Date of onset /hospital admission /diagnosis;
- Serotype.

Baseline characteristics of records with missing serotype will be compared to records without missing serotype in order to assess the bias due to differential serotyping by vaccination status.

For all the other variables, baseline characteristics of records with missing data will be compared to records without missing data. If there is no evidence of bias in the missing data, the distribution of IPD/SpCAP cases with known data will be applied to the cases with missing results. If a high proportion of data are missing and/or there is no evidence of bias in the missing data, and variables that are considered good predictors of the missing data are available, multiple imputation using chained equations can be used to replace missing values.

- Each study site to describe the data cleaning process and the management of missing data
- ► Each study site to specify the percentage of missing by variable collected and assess differences between serotyped and non-serotyped IPD/SpCAP cases.

TECHNICAL DOCUMENT – Protocol on effectiveness of Pneumo vaccines in elderly

5.2 Descriptive analysis

VT cases and NVT controls will be described by baseline characteristics (age, gender, clinical presentations, length of hospital stay, underlying conditions, vaccination). Baseline characteristics are compared in unmatched studies using the chi-square test, Fisher's exact test, t-test or the Mann-Whitney test (depending on the nature of the variable and the sample size). In matched studies, characteristics of cases and controls are compared using McNemar's chi-square test, paired t-test, conditional logistic regression, or the Wilcoxon signed-rank test (depending on the nature of the variable and the number of controls).

In addition, the association between vaccination status and baseline characteristics will be also measured for cases due to vaccine serotypes and due to non-vaccine serotypes.

► Each study site to specify the descriptive analysis planned

5.3 Measure of association

Vaccine effectiveness will be computed as 100% X (1 – the odds of vaccination in VT cases / odds of vaccination in NVT controls). An exact 95% confidence interval will be computed around the point estimate. The crude and adjusted estimates of vaccine effectiveness will be provided.

The VE will be computed for all exposures mentioned above.

5.4 Stratified analysis

Analysis will be stratified according to age group, year of diagnosis and any other variable relevant for the study setting depending on the sample size (e.g. gender, underlying diseases, influenza vaccination, etc.).

Effect modifiers should be assessed one by one, comparing the OR across the strata of baseline characteristics.

Confounding factors will be identified by comparing crude and adjusted OR for each baseline characteristic.

► Each study site to specify the stratified analysis planned

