4.5.1 Case definitions

For the primary outcome, a case is a hospitalised person eligible for PPSV23 and/or PCV13 vaccination confirmed with an IPD according the ECDC case definition (below), in whom serotyping identified a vaccine serotype (PCV13 or PPSV23 IPD/SpCAP cases). The EC 2008 case definition should be used to recruit IPD cases²²:

PNEUMOCOCCAL INVASIVE DISEASE(S) (Streptococcus pneumoniae)

Clinical criteria

Not relevant for surveillance purposes

Laboratory criteria

At least one of the following three:

- Isolation of Streptococcus pneumoniae from a normally sterile site
- Detection of Streptococcus pneumoniae nucleic acid from a normally sterile site
- Detection of Streptococcus pneumoniae antigen from a normally sterile site

Epidemiological criteria

NA

Case classification

A. Possible case

NA

B. Probable case

NA

C. Confirmed case

Any person meeting the laboratory criteria

For secondary outcomes, the case is defined as above for the primary outcome, and in addition:

- A specific vaccine serotype is identified (this can be a vaccine serotype or vaccine related serotype);
- A clinical manifestation is identified as: meningitis, pneumonia, bacteraemia and others;
- Severity is assessed according to: ICU admission and/or length of hospital stay >14 days and/or death within 30 days.

²² European Commission, Commission Decision 2008/426/EC of 28 April 2008 amending Decision 2002/253/EC laying down case definitions for reporting communicable diseases to the Community network under Decision No 2119/98/EC of the European Parliament and of the Council (notified under document number C(2008) 1589)

► Each study site to state the case definitions for each primary and secondary outcome according to data collected.

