4.7 Confounding factors and effect modifiers

Individual data collection is required for all IPD cases for surveillance purposes. A minimum set of variables to be collected in the enhanced surveillance systems are included in the table 3. Efforts should be made to harmonise the data collected by all sites.

To control for differences in the characteristics of VT-IPD cases and NVT-IPD controls, information on potential confounding factors should be collected. Those factors will include:

- Age;
- Gender;
- Time of diagnosis (year or month);
- Underlying conditions and other risk factors included in the recommendation for pneumococcal vaccination as defined Table 3 (end of the document). A minimum set of data on high risk conditions will be collected. The sites can include additional data if available;
- Functional status (Barthel index or other criteria available in the site);
- Influenza vaccination in the current season.

Other confounding factors can be included in addition to those already collected for IPD surveillance: number of children in the family, indicators of socio-economic status, smoking history etc.

► Each study site to define the variables used to identify potential confounding factors or effect modifiers and source of identification if different than data collected for surveillance purposes.

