5.5 Multivariable analysis

A multivariable (conditional if matched) logistic regression analysis will be conducted to control for identified confounding factors (such as age, gender, year of notification, underlying chronic conditions, etc.). Odds ratios and standard errors will be obtained. Variables will be tested for multicollinearity. Interactions will be tested using the likelihood ratio test or Wald's test and will be included in the model if significant at the 5% level. Factors other than statistical significance will also be used as criteria for inclusion of an interaction term.

► Each study site to describe the type of multivariable analysis planned.

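### Section 5.4 screens every baseline characteristic as a confounder, and the only list of these (5.2) includes length of stay and clinical presentation; the screen should be tied to the pre-infection variables of 4.7

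*Protocol*

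**What the plan says.** The adjusted VE is reached in three steps in the protocol.

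- **5.2 Descriptive analysis** gives the only list of the characteristics concerned: "VT cases and NVT controls will be described by baseline characteristics (age, gender, clinical presentations, length of hospital stay, underlying conditions, vaccination".
- **5.4 Stratified analysis** uses the same term as a selection rule: "Confounding factors will be identified by comparing crude and adjusted OR for each baseline characteristic". It uses the term for effect modifiers too: "Effect modifiers should be assessed one by one, comparing the OR across the strata of baseline characteristics".
- **5.5 Multivariable analysis** puts whatever was identified into the model: "logistic regression analysis will be conducted to control for identified confounding factors".

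Two items on the 5.2 list are outcome variables elsewhere. Clinical manifestation defines a secondary outcome in 4.5, and 4.5.1 says: "Severity is assessed according to: ICU admission and/or length of hospital stay >14 days and/or death within 30 days".

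Section 4.7 approaches confounding separately: "information on potential confounding factors should be collected. Those factors will include" age, gender, time of diagnosis, underlying conditions and risk factors, functional status and current-season influenza vaccination. Neither stay nor presentation is there. The list is open: "Other confounding factors can be included in addition to those already collected for IPD surveillance". Section 5.4 does not cite it.

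**The concern.** A confounder of vaccination and serotype group has to be in place before the infection. Length of stay and clinical presentation are not: both follow infection with a vaccine-type (VT) or non-vaccine-type (NVT) strain. They may depend on serotype, on frailty (which may also drive vaccination), and on a milder course in vaccinated VT patients. Conditioning on such a variable can move the OR when there is no confounding at all. A rule that compares crude with adjusted OR would read that movement as confounding.

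At stake is the adjusted VE. This is a generic protocol that sites adapt, and a pooled EU/EEA analysis is planned (section 8). One site could screen the 5.2 list and another the 4.7 list, so adjusted estimates resting on different covariates, some of them unsuitable, could be pooled.

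**Working it through.** The protocol has no figure to reproduce here. The check is textual first, then an illustration of size.

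**1. The sections side by side**

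| Section | Role | Variables named |
|---|---|---|
| 4.7 | Potential confounders to collect | Age, gender, time of diagnosis, underlying conditions, functional status, influenza vaccination; sites may add |
| 5.2 | Baseline characteristics, for description | Age, gender, clinical presentation, length of stay, underlying conditions, vaccination |
| 5.4 | Strata, then confounder screen | Strata: age group, year, gender, underlying diseases, influenza vaccination. Screen: each baseline characteristic |
| 5.5 | Model covariates | Age, gender, year of notification, chronic conditions, and an open end |

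Only 5.2 names post-infection variables, but its term is the one that 5.4 uses for the screen.

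**2. When adjusting for stay moves the OR**

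Let L be stay over 14 days (yes or no). Within stratum l:

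OR(l) = OR × [P(l | VT, vac) × P(l | NVT, unvac)] / [P(l | VT, unvac) × P(l | NVT, vac)]

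Inputs from 4.8: VT share 0.60, VE 0.60 and coverage 0.5 (both within Table 4). The probabilities of a long stay are assumptions; the protocol gives none.

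- *Stay depends on serotype group only* (0.45 in VT, 0.30 in NVT). The bracketed ratio is 1 in both strata, so VE stays at 0.60.
- *Vaccination shortens stay in VT only* (0.45 falls to 0.25; NVT 0.30 throughout). Long stay: 0.4 × (0.25 × 0.30)/(0.45 × 0.30) = 0.222, VE 0.778. Short stay: 0.4 × (0.75 × 0.70)/(0.55 × 0.70) = 0.545, VE 0.455. The Mantel-Haenszel summary is VE 0.580.
- *Stay longer in the vaccinated of both groups* (VT 0.60 vs 0.45; NVT 0.40 vs 0.30). Long stay: 0.4 × (0.60 × 0.30)/(0.45 × 0.40) = 0.400. Short stay: 0.4 × (0.40 × 0.70)/(0.55 × 0.60) = 0.339. The summary is VE 0.636.

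Over coverage 0.3 to 0.7 and VE 0.5 to 0.7, the shifts in these three settings (with the VT probability falling to 0.35, 0.25 or 0.15 in the second) ran from about −4 to +5 points.

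**3. Where frailty drives both stay and vaccination**

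All inputs are assumed: 40% frail; coverage 60% in the frail and 30% in others; VT:NVT ratio 1.5 in the unvaccinated whatever the frailty, so frailty does not confound. Log-odds of stay over 14 days = −1.0 + f × frail + s × VT + i × VT × vaccinated. Logistic regression of VT on vaccination was fitted to the expected cells. The crude VE equals the true VE in every row.

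| f | s | i | True VE | Stay-adjusted VE | Stay and frailty adjusted |
|---|---|---|---|---|---|
| 1.0 | +0.7 | 0 | 50% / 20% | 52.3% / 23.7% | 50% / 20% |
| 1.5 | +0.7 | 0 | 50% / 20% | 53.2% / 25.0% | 50% / 20% |
| 1.0 | −0.7 | 0 | 50% / 20% | 47.9% / 16.7% | 50% / 20% |
| 0 | +1.0 | −1.4 | 50% / 20% | 45.4% / 12.5% | 45.4% / 12.5% |

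The largest upward shift is 25.0 − 20 = 5.0 points and the largest downward shift is 20 − 12.5 = 7.5 points. On the OR scale the changes are about 4% (0.521/0.500 = 1.042) to 9% (0.546/0.500 = 1.092). Intercepts of −1.5 and −0.5 give similar shifts. Clinical presentation was not quantified.

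**The case against.** The strongest reply is that the 5.2 list was never meant as the candidate list. It stands in a descriptive section, and it contains vaccination, which cannot be screened as a confounder of itself. The candidates are in 4.7, and 5.5 illustrates them in the same spirit: "control for identified confounding factors (such as age, gender, year of notification, underlying chronic conditions, etc". Each of these sections also asks the site to specify its own analysis, and 5.3 reports crude beside adjusted VE, so a misstep would be visible. This largely stands. A reader might infer that the protocol plans to adjust for length of stay or presentation; it does not. What remains is that 5.4 sets a rule over an undefined term whose only listing is the wrong one.

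Three further objections concern size.

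- The frailty-driven shifts disappear once frailty is in the model, and 4.7 names functional status. This is correct. However, a change-in-estimate screen would not itself select frailty in those settings, where it does not confound, and Table 3 has no named variable for functional status (a catch-all row lets sites add one).
- Section 5.4 gives no threshold. Under a 10% change rule (an assumption), none of the stay effects above would be retained. That is fair, and a threshold may be left to the SAP or the site protocol.
- Stay may stand in for an unmeasured confounder such as frailty, so adjusting could remove some real confounding. That is possible, but the rule cannot distinguish that case from the others.

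A reader might also infer that in the analysis of VE by severity the outcome would become a covariate. The protocol does not support this. The dependent variable is always VT versus NVT (5.3), and severity and manifestation enter by restricting cases and controls (4.5.2). In a manifestation-specific analysis, presentation is constant.

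**Conclusion.** The point holds as a defect of wording with a possible effect on the estimate. Read literally, 5.2 and 5.4 make length of stay and clinical presentation candidates for adjustment, although both arise after infection and define secondary outcomes. The wording conflicts in substance with 4.7, and nothing in 5.4 resolves the conflict.

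It would go too far to conclude that the adjusted VE will be biased. Bias needs a site to follow the literal reading, and it needs stay to relate to vaccination differently in VT and NVT patients, directly or through frailty that is left out. If both hold, the assumed inputs give shifts of about 2 to 8 points, upward or downward. The shift is zero if stay depends on serotype group only. The part that survives adjustment for frailty rests on one assumed scenario, in which vaccination shortens stay in VT patients (50% to 45.4%, 20% to 12.5%). Severity: minor to moderate.

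**What to change.** - **5.4:** replace *each baseline characteristic* by *each pre-infection characteristic defined under 4.7 (including site additions)*, and apply the same limit to the effect-modifier sentence.
- **5.4 or 5.5:** state that clinical presentation, length of stay, ICU admission and death are not adjustment candidates. They serve only for description and for defining or restricting the secondary-outcome analyses.
- **5.2:** list clinical presentation and length of stay as features of the episode, and vaccination as the exposure, apart from the baseline characteristics.

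The cost is a few wording changes. No new data are needed, no patients are lost, and the descriptive tables keep the same content.

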5.5 Multivariable analysis

A multivariable (conditional if matched) logistic regression analysis will be conducted to control for identified confounding factors (such as age, gender, year of notification, underlying chronic conditions, etc.). Odds ratios and standard errors will be obtained. Variables will be tested for multicollinearity. Interactions will be tested using the likelihood ratio test or Wald's test and will be included in the model if significant at the 5% level. Factors other than statistical significance will also be used as criteria for inclusion of an interaction term.

► Each study site to describe the type of multivariable analysis planned.

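### Section 5.5 lets significance-tested interactions into the model that gives the adjusted VE, without saying which quantity is then the adjusted VE

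*Protocol*

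**What the plan says.** Section 5.3 promises two summaries: "The crude and adjusted estimates of vaccine effectiveness will be provided". It adds that "An exact 95% confidence interval will be computed around the point estimate".

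Section 5.4 screens for effect modification factor by factor: "Effect modifiers should be assessed one by one, comparing the OR across the strata of baseline characteristics". The strata are age group, year of diagnosis and any other variable relevant to the setting.

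Section 5.5 then describes the logistic model used to control confounding, with an open list of covariates: "such as age, gender, year of notification, underlying chronic conditions, etc". On interactions it says "Interactions will be tested using the likelihood ratio test or Wald's test" and that they "will be included in the model if significant at the 5% level". The next sentence qualifies this: "Factors other than statistical significance will also be used as criteria for inclusion of an interaction term". Those other factors are not named. The section closes by handing detail to the sites: "Each study site to describe the type of multivariable analysis planned".

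Section 4.7 lists six groups of potential confounders or effect modifiers, one of which (underlying conditions) can be split into many flags in Table 3. Nowhere does the main text say how VE is summarised once an interaction is in the model.

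**The concern.** The general objective (section 3.1) is VE in people aged 65 and over; VE by age group is secondary (section 3.2). Once a vaccination-by-covariate product is in a logistic model, the vaccination coefficient is no longer the overall log odds ratio. It is the log odds ratio at the reference level of that covariate. A rule that admits such terms when they pass a test lets the data decide what the adjusted VE measures. The stratum is singled out because its estimate looked different, and the model-based interval ignores that selection.

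The alternative reading, in which stratum-specific VEs are reported after a significant interaction, avoids the mislabelled coefficient. It still replaces the adjusted overall VE with subgroup differences that may be chance.

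Section 8 foresees a pooled EU/EEA estimate. Sites applying the rule to their own data can keep different terms, so their adjusted VEs need not estimate the same quantity.

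**Working it through.** **Inputs from the protocol.** Test level 0.05 per interaction (5.5). No number of candidate interactions is given, so k = 1 to 10 is an assumption. The sample sizes are two Table 4 rows: 356 cases and 238 controls (coverage 0.5, VE 0.5), and 354 and 236 (coverage 0.3, VE 0.6).

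**Check that the Table 4 rows are sound.** With OR = 1 - VE, p0 = coverage and p1 = p0·OR/(1 - p0 + p0·OR), cases = [1.96/ln((OR + 0.2)/OR)]² × [1/(p1(1 - p1)) + 1.5/(p0(1 - p0))]. For coverage 0.5 and VE 0.5, p1 = 1/3, so (1.96/ln 1.4)² × (4.5 + 6) = 33.93 × 10.5 = 356. For coverage 0.3 and VE 0.6 the result is 354. Both match the table.

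**Chance of keeping at least one false interaction.** With k independent tests this is 1 - 0.95^k: 5% (k = 1), 14% (3), 23% (5), 26% (6), 40% (10).

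**Why the retained coefficient misleads.** Take one binary covariate with prevalence q and no true interaction. Let b0 and b1 be the stratum log odds ratios, with variances proportional to 1/(1 - q) and 1/q. The interaction estimate is b1 - b0, and its correlation with b0 is -√q. Given that the interaction passes at 5%, the 95% interval for b0 covers the true value with probability 84% (q = 0.2), 79% (0.3), 66% (0.5) or 51% (0.7), integrating the bivariate normal over |z| > 1.96. The main-effects estimate is, to the same approximation, uncorrelated with the interaction and is unaffected.

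**Simulation.** The model was a logistic regression of vaccine-type versus non-vaccine-type disease on vaccination and k independent binary covariates, with the same VE in all strata. Each vaccination-by-covariate term was Wald-tested alone at 5% and significant terms were kept (1,500-2,500 replicates). Coverage of the overall VE by the Wald 95% interval of the vaccination coefficient:

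| k | 20% prevalence | 30% | 50% | 70% |
|---|---|---|---|---|
| 1 | not run | 93-94% | 93-94% | not run |
| 3 | not run | 92-93% | 90-91% | not run |
| 5 | not run | 90-91% | 87% | not run |
| 6 | 92% | 90-91% | 86% | 83% |
| 10 | 91% | 87% | 82-83% | 76% |

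Among the runs at 30% and 50% prevalence in which an interaction was kept, coverage was about 61-81%, in line with the 66-79% from the formula.

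**Does correcting the test level help?** With Bonferroni and 50% prevalence, false retention falls to about 5%, but coverage reaches only 92.3% (k = 6) and 91.6% (k = 10). The formula shows why: terms that pass 0.05/6 are rarer but more extreme, so coverage given retention drops to 43%. Overall, 0.951 × 0.95 + 0.049 × 0.43 = 0.925.

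**What does help.** In the same runs, the main-effects VE, and the VE averaged over strata after keeping the interactions, both had coverage of about 94-96% (single runs 93.5-95.6%).

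**The case against.** The strongest reply is that this is a generic protocol. Section 5.5 asks each site to describe its own multivariable analysis, and a list of interactions often belongs in a site protocol or SAP. That would answer a complaint about missing detail. It does not answer this one, because the 5% inclusion rule is itself written into the generic text that sites are asked to adapt.

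Section 5.5 also says that significance is not the only criterion. That is true, and the simulated mechanical rule is therefore not exactly the documented one. But the added criteria are unnamed, could admit terms as well as keep them out, and do not say which VE is reported.

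Four stronger readings are tempting, and the document does not support them:

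- **Every vaccination-by-covariate term is tested.** The text says only that interactions are tested, with no list or number.
- **The plan's interval has one definite, badly reduced coverage.** The loss depends on the assumed number and prevalence of covariates. It arises only if the bare vaccination coefficient is reported, which sections 5.3 to 5.5 do not say. Appendix 1, for the screening method, follows effect modification with a stratified analysis, which points towards stratum VEs.
- **The overall VE vanishes.** Section 5.3 always provides a crude VE; what can be lost is the adjusted overall VE.
- **The fault is the uncorrected 5%.** Bonferroni leaves coverage near 92%, so the fault is the unfixed estimand.

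**Conclusion.** The point stands in this limited form: section 5.5 makes the meaning of the adjusted VE depend on a significance test and does not define it afterwards. False retention affects a minority of analyses, about a quarter with 6 candidates. For the reference-stratum reading, coverage of 86-92% is the central range (6 binary covariates, 20-50% prevalence), and about 76-94% spans all settings tried.

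These figures assume independent binary covariates, no true effect modification, Wald intervals and a purely significance-driven rule. Rare condition flags would do less damage than balanced covariates. If VE were averaged over strata there would be no material loss, but the protocol does not ask for that. The problem of comparing sites in the pooled analysis needs no simulation; it follows from the rule and the open list.

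**What to change.** State in section 5.5 that the primary adjusted VE comes from the model with vaccination and the confounders as main effects (or is standardised over strata), and that no vaccination-by-covariate term is added to that model on the basis of a significance test.

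Examine effect modification in separate models, for a short list fixed in advance and common to all sites, for example age group and immune status. Report stratum VEs with the interaction p-value, labelled exploratory, and always beside the overall adjusted VE.

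Keep time since vaccination as an analysis by exposure category under section 5.6.2. It should not be on the interaction list, because it is undefined in the unvaccinated.

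The cost is a few sentences and no extra data. If strong true effect modification exists, the overall VE is an average over strata, but the stratum VEs are still reported.
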